7.2 Statistical Hypothesis

There is no hypothesis testing in the phase 2 study; where statistical methods are applied, the emphasis will be on estimation with 95% CIs.

7.3 Sample Size Determination

The sample size is based on clinical considerations to provide sufficient safety information for the analysis of the primary safety objective. With 75 participants randomly assigned to each priming vaccination dose group but with as few as 25 participants randomly assigned to individual booster vaccine groups [Table 7-3](#) presents estimated probability to detect at least one adverse event at various incidence rates by possible sample size in this study. The estimated probability was calculated using a formula as below.

$$p = 1 - (1 - R)^N$$

where R = incidence rate and N = sample size.

If the incidence rate of an adverse event is 1%, the probability to detect one event in 75 vaccinated participants is 52.9%, and the probability of detecting one event in 25 vaccinated participants is 22.2%; however, this probability will be 95.1% in a sample size of 300 in each Age Cohort. See more details and scenarios in the table below.

Table 7-3 Probability to Detect at Least One Adverse Event by Incidence Rate of Event and Sample Size

Rate (%)	N=25	N=75	N=150	N=225	N=300
0.01	0.002497002	0.007472	0.014889	0.02225	0.029556
0.1	0.024702287	0.072291	0.139357	0.201574	0.259293
1.0	0.222178641	0.529413	0.778548	0.895788	0.950959
2.0	0.39653527	0.780236	0.951704	0.989386	0.997667
5.0	0.722610427	0.978656	>0.999	>0.999	>0.999
10.0	0.928210201	>0.999	>0.999	>0.999	>0.999

The study plans to randomize 75 participants to each Study Group within each Age Cohort. Assuming a geometric coefficient of variance (CoV) of 180% (SD of 1.2 on loge scale), a sample size of 75:75 will provide a >99% power to detect 2-fold increase in antibody titers in ARCT-021 Study Groups versus placebo Study Groups. These power analyses were performed using PASS Version 15 software.

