5 STUDY TREATMENTS

5.1 Method of Assigning Participants to Study Groups

Assignment of participants to Study Groups will proceed through the use of an interactive response technology (IRT) system. The site personnel (study coordinator or specified designee) will be required to enter or select information including but not limited to the password, the protocol number, participant age and the participant code (a unique number identifying the participant). The site personnel will then be provided with a vaccine assignment and randomization number. The IRT system will provide a confirmation report containing the participant code, randomization number, and study intervention allocation assigned. The confirmation report must be stored in the site's files.

Additional guidance relating to study vaccine assignment is included in the Investigator Site File.

The Study Group assignments are summarized in [Synopsis Table 1-1](#). Participants enrolled in this study (N=600) will be stratified by age (younger, older; N=300 in each age group). Within each age group, the participants will be randomly assigned to receive ARCT-021 or placebo for the primary vaccination (3:1 randomization ratio), which will consist of 2 injections separated by 28 days (Day 0 and Day 28). At Day 208, participants will be randomly assigned to ARCT-021, ARCT-154, ARCT-165, or (for Study Groups 1, 2, 3 only) placebo for a third (booster) dose of study vaccine given 180 days after second study vaccination (ie, on Day 208). The randomization ratio of ARCT-021, ARCT-154, ARCT-165, and placebo will be 1:1:1:1 for Study Groups 1, 2, 3, and the randomization ratio of ARCT-021, ARCT-154, and ARCT-165 will be 1:1:1 (no placebo assignment) for any remaining participants in Study Group 4.

Participants who complete study procedures through Day 98 will be offered the opportunity to determine whether they are eligible for study re-enrollment to ensure dosing with ARCT-021.

After Day 98 and until Day 198, participants will be contacted to determine whether they are interested, if eligible, in re-enrolling in the study in order to receive active study vaccine.

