For those participants interested in receiving ARCT-021 provided by the Sponsor, an unblinded team member will confirm whether the participant has been assigned to Study Group 4 (placebo) or ARCT-021 (Study Groups 1, 2, or 3). Participants who request to re-enroll in the study but whose treatment assignments are determined to be in Study Groups 1, 2, and 3 will be informed they have already received ARCT-021 and will be advised to continue to remain on the study schedule.

Participants who intend to exit the study to seek approved COVID-19 vaccine will be allowed, after the approval of protocol version 4.0, to receive these vaccines. See [Section 4.2.3](#) for additional guidance.

Participants in Study Group 4 who have not otherwise met withdrawal criteria for study vaccine will sign a consent form, will undergo Early Termination Visit, will be assigned a new participant ID number, and will re-enter the study at Day 0. Re-enrolled participants will be randomly assigned to Study Groups 1, 2, and 3.

Arcturus Therapeutics, Inc.
Protocol ARCT-021-04, Version 6.0

ARCT-021
09 March 2022

Study vaccine will be administered in an observer-blind fashion. Participants will be followed for safety and immunogenicity through 570 days after first vaccination. Participation in the study past Day 388 is optional for participants enrolled in the United States. For participants enrolled in Singapore, participation through the Early Termination Visit is expected. At a subset of clinical sites, all enrolled participants will also undergo blood sampling for evaluation of CMI responses.

Vaccine doses will be assigned as shown in [Synopsis Table 1-1](#) and illustrated in [Synopsis Figure 1-2](#).

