7.1 Estimands and Intercurrent Events

Possible intercurrent events are presented in [Table 7-1](#).

Table 7-1 Intercurrent Event Types

Label	Intercurrent Event (IcEv) Type
IcEv1 (Death)	Death due to any cause (including pneumonia) other than COVID-19.
IcEv2 (Missed dose)	Does not receive the second or booster vaccinations at Day 28 and Day 208, respectively.
IcEv3 (Immune-modifying)	Use of immune-modifying drugs or non-study vaccines which interfere with immunogenicity.
IcEv4 (Early infection)	Antigens or antibodies indicating exposure to SARS-CoV-2 prior to vaccination or early infection before Day 7. (This IcEv is particularly relevant to assessing immunogenicity.)
IcEv5 (Study infection)	Develops COVID-19 or asymptomatic SARS-CoV-2 infection on or after Day 7. (This IcEv is particularly relevant to immunogenicity and CESI events.)

Attributes for the primary safety and immunogenicity estimands with strategies for intercurrent events (IcEvs) are presented in [Table 7-2](#).

Table 7-2 Primary Safety and Immunogenicity Estimands With Rationale and Strategies to Address Intercurrent Events

Estimand Label	Estimand 1 (Safety)
Estimand Description	Count and percentage of vaccinated healthy adults who would develop MAAEs, NOCDs, SAEs, AEs leading to discontinuation/withdrawal, solicited AEs, and unsolicited AEs: These will be evaluated after each dose of study vaccine by priming vaccine study group (Group 1, 2, 3, and 4) and by booster vaccine received (ARCT-021, ARCT-154, ARCT-165, or placebo). A treatment policy strategy is used for assessing safety irrespective of an early infection within 7 days after the first vaccination or an infection during the study or missed subsequent vaccination. Infections and death are included in the endpoint (composite strategy).
Target Population	Participants receiving at least 1 dose of study vaccine (as defined by eligibility criteria).
Endpoint	Occurrence of MAAEs, NOCDs, AEs leading to discontinuation/withdrawal, SAEs, solicited, or unsolicited AEs: 
 Solicited AEs within 7 days of each vaccination (by Toxicity Grade, Appendix 13.4): Day 7, Day 35, Day 215 Unsolicited AEs within 28 days of each vaccination (by mild/moderate/severe severity): Day 28, Day 56, Day 236 MAAEs, NOCDs, SAEs, AEs leading to discontinuation/withdrawal from Vaccination 1 to Prior to Vaccination 2, Vaccination 2 to Prior to Booster Vaccination, Overall Prior to Booster Vaccination, and Post-booster Vaccination

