7.6.7 Data Analyses from Re-Enrolled Participants

All safety data collected after active vaccination from Study Group 4 participants who are re-enrolled into Study Groups 1, 2, or 3 (ARCT-021-exposed study groups) will be summarized and presented by dose group and overall separately from those participants who complete the study as originally randomized. Participant level data will be displayed in listings, separately from data in originally randomized.

Immunogenicity data collected after active vaccination from Study Group 4 participants who are re-enrolled into Study Groups 1, 2, or 3 (ARCT 021-exposed study groups) will be listed. This data may be summarized and presented by dose group and overall separately from those participants who complete the study as originally randomized. If summarized, it will be reported in an addendum to the CSR.

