4.2. Sample Size

The sample size is based on clinical considerations to provide sufficient safety information for the analysis of the primary safety objective. With 75 participants randomly assigned to each priming vaccination dose group but with as few as 25 participants randomly assigned to individual booster vaccine groups Table 4-2 presents estimated probability to detect at least one adverse event at various incidence rates by possible sample size in this study. The estimated probability was calculated using a formula as below:

$$p = 1 - (1 - R)^N$$

where R = incidence rate and N = sample size.

If the incidence rate of an adverse event is 1%, the probability to detect one event in 75 vaccinated participants is 52.9%, and the probability of detecting one event in 25 vaccinated participants is 22.2%; however, this probability will be 95.1% in a sample size of 300 in each Age Cohort. See more details and scenarios in the table below.

Table 4-2 Probability to Detect at Least One Adverse Event by Incidence Rate of Event and Sample Size

Rate (%)	N=25	N=75	N=150	N=225	N=300
0.01	0.002497002	0.007472	0.014889	0.02225	0.029556
0.1	0.024702287	0.072291	0.139357	0.201574	0.259293
1.0	0.222178641	0.529413	0.778548	0.895788	0.950959
2.0	0.39653527	0.780236	0.951704	0.989386	0.997667
5.0	0.722610427	0.978656	>0.999	>0.999	>0.999
10.0	0.928210201	>0.999	>0.999	>0.999	>0.999

The study plans to randomize 75 participants to each Study Group within each Age Cohort. Assuming a geometric coefficient of variance (CoV) of 180% (SD of 1.2 on log_e scale), a sample size of 75:75 will provide a >99% power to detect 2-fold increase in antibody titers in ARCT-021 Study Groups versus placebo Study Groups. These power analyses were performed using PASS Version 15 software.

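### The 25 given as the smallest booster group is the planned maximum for one tabulated cell (placebo-primed × age cohort × active booster), so the stated worst-case detection probability is slightly too favourable

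*Protocol*

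**What the plan says.** Protocol 7.3, repeated in SAP 4.2, sets 75 participants per priming group beside a booster phase "with as few as 25 participants randomly assigned to individual booster vaccine groups". It does not say which cell has 25 participants. The table that follows (Protocol Table 7-3, SAP Table 4-2) has an N=25 column, and the text says that for an event with a 1% rate "the probability of detecting one event in 25 vaccinated participants is 22.2" percent. The 75 is a within-cohort number: "The study plans to randomize 75 participants to each Study Group within each Age Cohort".

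Protocol 5.1 gives two booster splits. For the ARCT-021-primed groups, "The randomization ratio of ARCT-021, ARCT-154, ARCT-165, and placebo will be 1:1:1:1 for Study Groups 1, 2, 3". For placebo-primed participants the ratio "will be 1:1:1 (no placebo assignment) for any remaining participants in Study Group 4".

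Group 4 can shrink before Day 208. Between Day 98 and Day 198 its members may re-enter the study under a new number: "Re-enrolled participants will be randomly assigned to Study Groups 1, 2, and 3". Protocol 7.6.7 summarizes their later safety data "separately from those participants who complete the study as originally randomized". Protocol 4.2.2 stops further study doses after an off-study COVID-19 vaccine.

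SAP Table 4-1 keeps placebo-primed booster recipients in their own columns (E2, F2, G2). SAP 9.1.2.1 summarizes booster unsolicited adverse events by the eight priming-booster groups, with an overall summary for all participants and by age group.

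**The concern.** A reader takes the stated 25 as a floor: no booster group smaller than this, hence no detection probability worse than the N=25 column. If 25 is a best case for a cell that will be reported, the sensitivity statement is too favourable exactly where numbers are thinnest.

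That cell has some interest. Protocol 1.5 says ARCT-154 and ARCT-165 had not been in any clinical trial when Investigator's Brochure version 4.0 was finalized. Among participants analysed as originally randomized, F2 and G2 are the ones who receive these vaccines without ARCT-021 priming. A zero count in such a cell excludes less than the text implies.

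**Working it through.** **Inputs.** 75 per Study Group per age cohort (Protocol 7.3); booster splits 1:1:1:1 in Groups 1–3 and 1:1:1 in remaining Group 4 (Protocol 5.1); 579 enrolled against about 600 planned (Protocol 1.5, 3.1). The documents give no number re-enrolled and no allowance for dropout or missed boosters, so these are treated as a range.

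**Reproducing the plan.** With p = 1 − (1 − R)^N, R = 0.01 and N = 25, p = 1 − 0.99^25 = 0.222, as stated. Every cell of Table 7-3 reproduces. The 25 itself is 75/3, the Group 4 cell within one cohort. The other split, 75/4 = 18.75, does not give 25.

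**Planned cell sizes (average, no losses).**

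| Cell | Per cohort | Both cohorts |
|---|---|---|
| Placebo-primed × one active booster (E2, F2, G2) | 75/3 = 25 | 150/3 = 50 |
| ARCT-021-primed, regimens pooled × one booster (E1, F1, G1) | 225/4 = 56.25 | 450/4 = 112.5 |
| One priming regimen × one booster | 75/4 = 18.75 | 150/4 = 37.5 |

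**What lowers the 25.**

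- Enrollment: 579/8 = 72.4 per Study Group and cohort if the split is equal (assumed). Then 72.4/3 = 24.1.
- Re-enrollment of k Group 4 members in a cohort leaves (75 − k)/3: 24.7 at k = 1, 22.5 at 10%, 18.75 at 25%, 12.5 at 50%. The shares are assumptions. Re-enrolled data are summarized separately, so they do not refill the cell.
- Off-study vaccination and dropout act in the same direction. SAP 1 itself cites attrition and other COVID-19 vaccines as limiting interpretation beyond Day 56; the booster visit is Day 208.

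**Effect on detection, 1 − (1 − R)^N.**

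| True rate | N=25 | N=19 |
|---|---|---|
| 1% | 22.2% | 17.4% |
| 2% | 39.7% | 31.9% |
| 5% | 72.3% | 62.3% |
| 10% | 92.8% | 86.5% |

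N = 19 corresponds to (75 − 18)/3, that is, 18 of 75 gone. At 24.1 the 1% figure is 21.5%. If half of Group 4 left (assumed), N = 12.5 and it is 11.8%. The rate seen at least once with 95% probability, 1 − 0.05^(1/N), is 11.3% at N = 25 and 21.3% at N = 12.5.

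**Where 18.75 appears in planned tables.** When the SAP separates the priming regimens it pools the active boosters (A1, B1, C1) against placebo or no booster (A2, B2, C2). SAP 9.1.1 plans solicited events in that layout by age, so A2, B2 and C2 start at 18.75 per cohort before non-boosted participants are added. No planned table was found with one priming regimen × one active booster × age.

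**The case against.** The strongest reply is that 25 is no arithmetic slip, since 75/3 is exact, and that the cell is a minor one. The safety estimand in Protocol 7.1 groups participants "by booster vaccine received (ARCT-021, ARCT-154, ARCT-165, or placebo"), and the main ARCT-021-primed columns are far larger: at a 1% rate the detection probability is 43.2% at 56.25 and 67.7% at 112.5. Booster objectives are exploratory, nothing is tested, and the section sizes the study for the primary (priming) safety objective. The overall unsolicited-event summaries carry Clopper-Pearson intervals on actual denominators, so a zero in a small cell shows its own uncertainty. Going from 600 to 579 moves the 1% figure only from 22.2% to 21.5%.

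All of that stands, and it limits the size of the point. It does not rescue the wording: the sentence states a lower bound, the figure is an upper one, and E2, F2 and G2 by age are a planned safety display.

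Two stronger readings are tempting. A reader might infer that the booster arms hold only about 19 people. The documents do not support this: 75/4 describes a cell that the planned tables show only for the placebo-booster columns, which say nothing about detecting events after ARCT-154 or ARCT-165. A reader might also infer that any re-enrollment takes the placebo-primed booster groups below 25. That is true only within one cohort. Over both cohorts the cell starts at 50 and drops below 25 only if more than 75 of the 150 Group 4 participants leave.

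**Conclusion.** The point holds as a labelling fault with a small numerical consequence. The 25 is the planned size of one cell, placebo-primed × age cohort × active booster, under full enrollment and no loss. It is presented without that label as the minimum booster group size. The plan's own re-enrollment rule, the off-study vaccine rule and the achieved enrollment all push the cell below 25.

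For a 1% event the stated 22.2% becomes 21.5% from enrollment alone and 17.4% at N = 19. Anything lower depends on a re-enrollment or loss share that the documents do not give.

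The assumptions are an equal split of the 579 over eight Study Group × cohort cells and even booster allocation within a cohort. The figures are averages, so chance in the allocation could put an individual cell slightly above or below them. The documents do not support a conclusion that booster safety overall rests on cells this small.

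**What to change.** In SAP 4.2, or in the clinical study report if the SAP is not reopened, replace the phrase about as few as 25 with a statement that 25 is the planned maximum for the placebo-primed × age cohort × active-booster cell before re-enrollment, off-study vaccination or dropout.

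Protocol 4.2.4 ends study vaccination on 15 December 2021, so the achieved counts can be established. Give the detection probability for the smallest active-booster cell actually tabulated, alongside or in place of the N=25 column. The N=19 column above shows the form it would take.

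The cost is one sentence and one column. The stated sensitivity becomes less favourable; no analysis, table layout or study conduct changes.

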Estimand 2	
The GMT of total NAbs (primary) and GMC of BAbs (secondary) titers against SARS-CoV-2 from Day 14 up to Early Termination after initial priming vaccination with ARCT-021 and booster vaccinations (ARCT-021, ARCT-154, and ARCT-165) (exploratory) of each dose in healthy adults. Interest will lie in comparing the GMC of each dosing regimen to placebo (GMR).
 
The hypothetical strategy is used to estimate antibody levels had both scheduled vaccinations been received, and without any influence from immune-modifying drugs or non-study vaccines, or subsequent SARS-CoV-2 infection. See Table 7-2 for further details.
	mITT	Values below the limit of quantification (LOQ) or limit of detection (LOD) will be replaced by LOQ/2 and LOD/2, respectively.	
Total NAbs and BAbs levels will be summarized with descriptive statistics, including boxplots (on log scale versus time) by time point: Days 14, 28, 42, 56, 208, 236, Early Termination. GMTs with corresponding 95% CI will be provided at each time point. The 95% CIs will be calculated based on the t-distribution of the log-transformed values then back transformed to the original scale. GMFRs with corresponding 95% CI will be provided at each post-baseline timepoint over baseline. The 95% CIs will be calculated based on the t-distribution of the log-transformed values then back transformed to the original scale.
	
Supportive: For the priming vaccination period ANCOVA will be fitted to the natural log transformed antibody titers and antibody concentrations measured against SARS-CoV-2 with terms for treatment group, age group and natural log baseline titer by each post-vaccination immunogenicity visit. The geometric least squares mean (GLSM) and corresponding 2-sided 95% CI for each treatment group will be provided by visit. Geometric mean ratio (GMR), estimated by the ratio of GLSM, and the corresponding 95% CI will be provided to assess the difference between ARCT-021 vs. placebo groups at each visit.
 
Descriptive statistics, GMT/GMFRs based on t-distribution will be presented by the following analysis subgroups: age group, gender and country. ANCOVA models will be presented by gender and country.

Table 7-4 Summary of Statistical Methods and Supportive Analyses

Estimand Label	Estimand Description	Main Estimation			Supportive Analysis
		Analysis Set	Imputation/ Data/ Censoring Rules	Analysis Model/Method	

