7.6.4 Analysis of Primary and Secondary Immunogenicity Endpoints

7.6.4.1 Analysis of Immunogenicity Endpoint (GMT/GMC and GMR) (Estimand 2)

The primary immunogenicity analyses will be performed using the mITT set evaluating responses measured by neutralizing antibody assay. Secondary immunogenicity analyses will be performed using the mat set evaluating responses measured by binding antibody assays.

Total NAbs and BAbs titers will be summarized using descriptive statistics (number of subjects (n), median, minimum and maximum) by each time point: Baseline, Days 14, 28, 42, 56, 208, 236, Early Termination. Geometric mean titers (GMT) with corresponding 95% CIs will be provided. The 95% CIs will be calculated based on the t-distribution of the log-transformed values then back transformed to the original scale for presentation. GMTs and corresponding 95% CIs will be plotted at each timepoint. GMFRs with corresponding 95% CIs will be provided at each post-baseline timepoint over baseline. The 95% CIs will be calculated based on the t-distribution of the log-transformed values then back transformed to the original scale for presentation. GMFRs and corresponding 95% CIs will also be plotted at each timepoint. Analyses will be repeated by subgroups as follows: gender, age group

Arcturus Therapeutics, Inc.
Protocol ARCT-021-04, Version 6.0

ARCT-021
09 March 2022

(≥ 18 to < 56 and ≥ 56 years) and country. Scatter plots of NAbs and BAbs titers at specific time points will be presented.

For the priming vaccination period an analysis of covariance model (ANCOVA) will be fitted to the natural log transformed neutralizing antibody titers measured against SARS CoV 2 with terms for treatment group, age group (≥ 18 to < 56 and ≥ 56 years) (stratification factor at randomization) and natural log baseline titer by each post-vaccination immunogenicity visit. The geometric least squares mean (GLSM) and corresponding 2-sided 95% CI for each treatment group will be provided by visit. Geometric mean ratio (GMR), estimated by the ratio of GLSM, and the corresponding 95% CI will be provided to assess the difference between ARCT-021 vs. placebo groups at each visit. No adjustments for multiplicity will be carried out. ANCOVA analyses will be repeated by the following subgroups: gender and country.

The above summaries and analyses will be present for binding antibody concentrations as well.

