All CIs will be 2-sided and performed using a 5% significance level. No multiplicity adjustment will be made for this study where multiple treatment groups and endpoints are being evaluated.

All analyses adjusting for age group (≥ 18 to <56 years; ≥ 56 years) will use the values derived from age reported in the interactive response technology (IRT) which was used for randomization stratification.

Early termination visits will be summarized separately for the priming vaccination period and the booster vaccination period, respectively.

Analysis will be presented by study phase and study treatment group where applicable as per [Table 4-1](#) below:

Table 4-1 **Study Phase and Study Treatment Groups**

Study Phase	Study Treatment Groups	Shell Presentation of Treatment Group
Priming Vaccination	ARCT-021 7.5 µg - Placebo	A
	ARCT-021 5.0 µg - ARCT-021 5.0 µg	B
	ARCT-021 7.5 µg - ARCT-021 7.5 µg	C
	Placebo	D
Booster Vaccination	ARCT Priming - ARCT-021 Booster	E1
	Placebo Priming - ARCT-021 Booster	E2
	ARCT Priming - ARCT-154 Booster	F1
	Placebo Priming - ARCT-154 Booster	F2
	ARCT Priming - ARCT-165 Booster	G1
	Placebo Priming - ARCT-165 Booster	G2
	ARCT Priming - Placebo/No Booster	H1
	Placebo Priming - No Booster	H2
Priming Vaccination (Re-enrolled Subjects Only)	ARCT-021 7.5 µg - Placebo	A
	ARCT-021 5.0 µg - ARCT-021 5.0 µg	B
	ARCT-021 7.5 µg - ARCT-021 7.5 µg	C

For some summary tables of booster vaccination period, active boosters will be pooled, and treatment groups will be presented like the following:

Booster Vaccination	ARCT-021 7.5 µg - Placebo - ARCT Booster	A1
	ARCT-021 7.5 µg - Placebo - Placebo Booster/ No Booster	A2
	ARCT-021 5.0 µg - ARCT-021 5.0 µg - ARCT Booster	B1
	ARCT-021 5.0 µg - ARCT-021 5.0 µg - Placebo Booster/No Booster	B2
	ARCT-021 7.5 µg - ARCT-021 7.5 µg - ARCT Booster	C1
	ARCT-021 7.5 µg - ARCT-021 7.5 µg - Placebo Booster/No Booster	C2
	Placebo - ARCT Booster	D1
	Placebo - No Booster	D2

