8.2.2. Supportive Analyses of Primary and Secondary Immunogenicity Endpoints

8.2.2.1. Supportive Analyses of Estimand 2

To assess the magnitudes of the differences between the treatment groups (ARCT-021 vs. Placebo) in SARS-CoV-2 neutralizing antibody (NAbs) and SARS-CoV-2 binding antibody (BAbs) endpoints, an analysis of covariance (ANCOVA) model will be fitted to the natural log transformed neutralizing antibody titers measured against SARS CoV 2 with terms for treatment group, age group (≥ 18 to < 56 and ≥ 56 years) (stratification factor at randomization) and natural log baseline titer by each post-vaccination immunogenicity visit. No imputation of missing data will be done.

The geometric least squares mean (GLSM) and corresponding 2-sided 95% CI for the antibody titers for each treatment group will be provided by visit. The GLSM and corresponding 95% CI results in log-transformed scale estimated from the model will be back-transformed to obtain these estimates in the original scale. Geometric mean ratio (GMR), estimated by the ratio of GLSM and the corresponding 2-sided 95% CI will be provided to assess the treatment difference between ARCT-021 group vs. placebo group at each visit.

ANCOVA analyses will be performed for the priming vaccination period on mITT analysis set only.

8.2.2.2. Supportive Analyses of Estimand 3

The common difference of seropositivity and seroconversion rates and 95% CIs between each vaccine dose group and the placebo will be estimated using the Miettinen-Nurminen method with age group (≥ 18 to < 56 and ≥ 56 years) as stratification factor for each time point.

Miettinen-Nurminen analyses will be performed for the priming vaccination period on mITT analysis set only.

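### At two-sided 5%, the printed inputs give about 94% power for 75:75, not the stated >99%; the same inputs give 99.9% for 150:150 with age cohorts combined

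*Protocol*

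**What the plan says.** The sample size is justified on safety grounds: "The sample size is based on clinical considerations to provide sufficient safety information for the analysis of the primary safety objective". After the table of probabilities of seeing at least one adverse event, Protocol 7.3 adds a short statement about antibody titers. It first fixes what the number 75 means: "The study plans to randomize 75 participants to each Study Group within each Age Cohort". It then assumes a geometric CoV of 180%, which it equates to an SD of 1.2 on the natural-log scale, and states that "a sample size of 75:75 will provide a >99% power to detect 2-fold increase in antibody titers in ARCT-021 Study Groups" compared with placebo. It names the software but no alpha, sidedness or test. SAP 4.2 carries the same text.

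Two other statements bear on how to read this. Protocol 7.2 says "There is no hypothesis testing in the phase 2 study". SAP Section 4 says "All CIs will be 2-sided and performed using a 5% significance level".

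The planned between-group comparison of titers is a supportive ANCOVA. Protocol Table 7-4 gives it "terms for treatment group, age group and natural log baseline titer by each post-vaccination immunogenicity visit", and SAP 8.2.2.1 says "ANCOVA analyses will be performed for the priming vaccination period on mITT analysis set only". With 75 per Study Group in each of two age cohorts, that model compares 150 with 150 for each regimen against placebo.

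**The concern.** The power statement can be recomputed almost entirely from what is printed: effect, SD and group sizes are given, and only alpha and sidedness are missing. At the plan's own two-sided 5% convention the result falls about 5 percentage points short of the claim. As a miss rate, that is about 6% rather than under 1%.

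The 75:75 comparison is one that the SAP plans to report. SAP 8.2.2.3 drops the age term for ANCOVA models run by age group, and the table in SAP 8.4 marks the ANCOVA for the <56 and ≥56 groups. The protocol text is narrower ("ANCOVA analyses will be repeated by the following subgroups: gender and country"). A reader of the within-cohort results would naturally take >99% as describing them, and the figure could be carried into the study report.

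**Working it through.** **Inputs**

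| Input | Value | Source |
|---|---|---|
| Effect | 2-fold, so δ = ln 2 = 0.6931 | Protocol 7.3, SAP 4.2 |
| SD, loge scale | 1.2 | Protocol 7.3, SAP 4.2 |
| Group sizes | 75:75 | Protocol 7.3, SAP 4.2 |
| Alpha | two-sided 5% (not printed with the power figure; taken from the CI rule) | SAP Section 4 |
| Stated power | >99% | Protocol 7.3, SAP 4.2 |

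**Step 1. Do the CoV and the SD agree?** SD = √ln(1 + CV²) = √ln(1 + 1.8²) = √ln 4.24 = 1.202. They agree, so the SD is not the source of the gap.

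**Step 2. Try to reproduce the stated figure.** For an unadjusted two-sample t comparison:

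- Standard error = 1.2 × √(1/75 + 1/75) = 0.196.
- Noncentrality = 0.6931 / 0.196 = 3.54, with 148 degrees of freedom.
- Two-sided 5%: critical t = 1.976, power = **94.0%** (93.9% with SD 1.202). The normal approximation gives Φ(3.54 − 1.96) = 94.3%.
- One-sided 5%: critical t = 1.655, power = **97.0%**.
- One-sided 10%: power = 98.8%.

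None of these exceeds 99%.

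**Step 3. What would give 99% at 75:75?** Each of the following, taken alone, would do it:

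- alpha of about 0.23 two-sided, or 0.115 one-sided;
- at two-sided 5%, an SD of about 0.98 instead of 1.2;
- at two-sided 5%, an effect of about 2.33-fold instead of 2-fold.

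**Step 4. Which group sizes give >99% with the printed effect and SD (two-sided 5%)?**

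| Comparison | Sizes | Noncentrality | Power |
|---|---|---|---|
| One regimen vs placebo, one age cohort (as printed) | 75:75 | 3.54 | 94.0% |
| Smallest equal arms reaching 99% | 112:112 | 4.32 | 99.05% (111:111 gives 98.99%) |
| Three ARCT-021 groups vs placebo, one cohort | 225:75 | 4.33 | 99.1% |
| One regimen vs placebo, cohorts combined | 150:150 | 5.00 | 99.9% |

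**Step 5. Effect of smaller numbers.** The figures above are before exclusions. Protocol 1.5 reports 579 enrolled. If they were spread evenly over the eight group-by-cohort cells (an assumption; 579/8 ≈ 72), 72:72 gives 93.1%. If 20% of 75 per arm had no usable data (an assumption), 60:60 gives 88.1%.

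**The case against.** The strongest reply is that the faulty element may be the 75:75 and not the >99%. The sentence speaks of placebo Study Groups in the plural, although there is only one placebo group per cohort. It could therefore describe the two cohorts together, where 150:150 gives 99.9%. This is a plausible source, but the preceding sentence defines 75 as one Study Group within one Age Cohort, and the documents do not settle which calculation was run. What stands is that the printed n and the printed power do not belong together. A correction should therefore report both sizes.

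A second reply is that the planned comparison adjusts for log baseline titer, whereas the check is unadjusted. If 1.2 is the unadjusted SD, the adjusted SD is 1.2 × √(1 − ρ²). At 75:75 and two-sided 5% this gives 95.8% for ρ = 0.3, 98.2% for ρ = 0.5 and 99.3% for ρ = 0.6. The 99% mark is reached at about ρ = 0.57. No correlation is printed. A high one looks unlikely, because people with known prior infection are excluded at entry and the immunogenicity estimands exclude those with evidence of infection at baseline. If the sponsor did rely on such a correlation, it needs to be stated.

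Third, alpha is borrowed from the confidence-interval rule in a study with no hypothesis tests. That is true, but the conclusion does not hang on it: one-sided 5% and even one-sided 10% also fall short.

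Finally, enrollment is complete and the study has been terminated early, so nothing in the design can change. That limits the importance of the point but does not make the sentence correct.

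**Conclusion.** The concern holds, as a minor point. On the printed effect, SD and group sizes, an unadjusted two-sample comparison has 94.0% power at two-sided 5% (97.0% at one-sided 5%), against a stated figure above 99%. The two-sided 5% level is an assumption taken from the SAP's CI convention, but no conventional alpha brings 75:75 above 99%. The same inputs do support >99% for 150:150 with age cohorts combined, the planned size of the age-adjusted ANCOVA for each regimen against placebo. Which calculation produced the printed figure is not known. The damage is confined to a misstated planning figure, and 94% is still high power.

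**What to change.** In Protocol 7.3 and SAP 4.2, replace the power sentence with one that prints alpha and sidedness and gives both sizes. For example: *about 94% power for 75:75 within an age cohort (two-sided 5%, unadjusted two-sample t-test, before exclusions); >99% for 150:150 with age cohorts combined*. If the software run used other inputs, such as pooled groups or a baseline correlation, print those inputs instead so that the figure can be reproduced.

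The cost is one sentence in each document. Sample size, analyses and decision rules are unchanged.
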